8.8 Handling of Missing Values

Listwise deletion of observations with missing data is necessary to correctly calculate Cronbach's coefficient alpha and for the chi-square test, therefore listwise deletion will be used for the reliability analysis and chi-square analysis. All missing data will be quantified in the final report and possible biases for any missing data will be reported.

8.9 Statistical Analysis

Statistical analyses will be conducted in SAS® software, Version 9.4 or higher of the SAS System for Windows (Copyright © 2013 SAS Institute Inc.) or other appropriate statistical software. P<0.05 will be considered statistically significant.

All continuous variables will be summarized using the following descriptive statistics: (non-missing sample size), mean, standard deviation, median, maximum and minimum. The frequency and percentages (based on the non-missing sample size) of observed levels will be reported for all categorical measures. 95% confidence intervals will be calculated for all means. In addition to summary statistics for the full sample and for each of the four positions with the key variable of interest being the percentage of tests that passed and those that failed for the full sample and for each of the four rotational positions will be calculated.

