3 OBJECTIVES AND ENDPOINTS

OBJECTIVES	ENDPOINTS	JUSTIFICATION FOR ENDPOINT(S)

Primary Objective: To evaluate the FitRight® System sensor's ability to detect when an adult brief has absorbed enough liquid (~90-360 mL) normal saline via a simulated urinary void to trigger an alert to change the brief in the sitting, supine, and right or left side positions.
	
Primary Endpoint: The number of FitRight® System alerts when 90-360 mL normal saline has been absorbed into the brief in the sitting, supine, and right or left side positions.
	To determine the wetness/absorbency efficacy of the FitRight® Alert indicator in three positions

Secondary Objective: To determine the brief's residual volume capacity . In a subset of 22 participants, evaluate the FitRight® Brief after the brief has absorbed the maximum amount of liquid normal saline via a simulated
	
Secondary Endpoint: The weight of the filter paper after performing the rewet test with the FitRight® Brief after absorbing 360 mL of normal saline via a simulated void.
	To determine the brief's residual volume capacity for possible improvements to the FitRight® System.

OBJECTIVES	ENDPOINTS	JUSTIFICATION FOR ENDPOINT(S)
urinary void (360 mL) in the sitting position and then weighed via the rewet procedure.		

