8 STATISTICAL CONSIDERATIONS

8.1 Sample Size Determination

A sample size of 56 was chosen to evaluate the 95% confidence interval on the proportion of successful wetness alerts. The NCSS PASS procedure "Confidence Intervals for One Proportion" was used to solve for "CI width or distance from P to limit". It was assumed that the proportion of successes would be around 90% (0.85, 0.90 and 0.95 entered into PASS). Because testing will occur in 8 subgroups, the largest sample size that was a multiple of 8 that provided the most narrow 95% confidence limits was selected (N=56).

Rewet testing sample size: A convenient subset of the first 22 completed patients will be recruited for the rewet procedure. Patients will be considered complete if they have all data, for all three of the brief tests.

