8.2 Randomization

Patients were randomized into two equal groups of 28 by means of a SAS® software generated random seed number and randomization program (Copyright © 2013 SAS Institute Inc.) only for the side position. Twenty-eight patients will complete the test using their right side and 28 will complete the test using their left side. Practically, it will be impossible to blind the staff and patients to the left or right side, as it will be apparent. Thus, the randomization will only be blinded to the analyst to ensure an un bias analysis.

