8.9.1 Analysis of Primary Endpoints

The primary goal of this research study is to assess the reliability of the FitRight® Alert Indicator for the full sample and stratified by the four rotational positions, the three different fluid amounts,

and the combination of rotational positions and fluid amounts. Cronbach's coefficient alpha estimate's reliability by determining the internal consistency of a test or the average correlation of items within a test. The pass/fail values from this set of test runs will be compared to the derived variable of whether or not the test should have triggered an alert. Since the variables of interest are dichotomous (pass/fail), the coefficient alpha is equivalent to the Kuder-Richardson 20 (KR-20) reliability measure. It produces a correlation measure between 0 where a high KR20 coefficient (e.g., >0.90) is indicative of a homogeneous test. A reliability of 0.70 or higher for an acceptable rating and 0.80 or higher for a good rating.

In addition, a chi-square analysis will be conducted to determine if any association between rotational position and test status (pass/fail) exists. This analysis will be repeated to examine any possible associations between fluid added and test status (pass/fail).

Spearman correlation analysis will be used to examine possible associations between the key variables of triggered alert value (pass/fail), rotational position (sitting, supine, left side, right side), and fluid volume of 90 mL, 150 mL, 120 mL, and 120 mL with covariates of age, sex, and brief size. Additional t-tests or non-parametric tests will be employed to further examine any significant associations found in the correlational analyses between key and covariate measures.

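### The objective names three positions but the analysis uses four levels and specifies no pooled side estimate, so side-lying is reported only as two strata of 28

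*Combined protocol and SAP*

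**What the plan says.** **Three positions.** In Section 3 the primary objective and endpoint cover alerts "in the sitting, supine, and right or left side positions", and the justification column reads "To determine the wetness/absorbency efficacy of the FitRight® Alert indicator in three positions". The synopsis (1.1), the overall design (4.1) and the withdrawal section (5.4) agree: three briefs, one per position, the third on whichever side was allocated. Section 8.2 fixes the split: "Twenty-eight patients will complete the test using their right side and 28 will complete the test using their left side".

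**Four positions.** Section 8.5.1 defines the primary endpoint with left and right listed separately. Section 8.6 codes position 1 to 4, with left as 3 and right as 4. Section 8.5.3 stratifies the pass and fail percentages by that variable. Section 8.9 asks for "the percentage of tests that passed and those that failed for the full sample and for each of the four rotational positions". Section 8.9.1 plans the reliability analysis "stratified by the four rotational positions" and tests position against pass/fail by chi-square.

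**No combined side level.** The only derived variable in 8.7 indicates whether a test should have passed. Left and right come together only in the full sample, where they are mixed with sitting and supine.

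**Sample size.** Section 8.1 says "A sample size of 56 was chosen to evaluate the 95% confidence interval on the proportion of successful wetness alerts". It gives no target width and does not say whether the proportion is per position or overall.

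**The concern.** The primary objective treats side-lying as one position. Under the plan, two of the three positions each receive a pass percentage on 56 participants. The third is reported as two percentages on 28, with no summary for the position as a whole.

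Two consequences follow. First, the side results are less precise than the sitting and supine results, although the same number of side tests is performed. Second, the four-level variable also enters the reliability strata and the chi-square test. Those analyses therefore address left versus right as well as the three-position question, and the plan states no left-versus-right objective.

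**Working it through.** **Inputs**
- 56 participants (8.1), each tested once in each of three positions (4.1): 56 × 3 = 168 tests.
- Side allocation 28 right and 28 left (8.2).
- Assumed success proportions 0.85, 0.90 and 0.95 (8.1).

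**Results available per level**

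| Position | Objective (three levels) | Analysis (four levels) |
|---|---|---|
| Sitting | 56 | 56 |
| Supine | 56 | 56 |
| Side | 56 | left 28, right 28 |

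The split is consistent with the total: 28 + 28 = 56.

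**The plan's own figure.** N=56 cannot be reproduced, because 8.1 gives no target width. It is a multiple of 8 (8 × 7), but the interval keeps narrowing as N rises (Wilson width at 0.90: 0.174 at 48, 0.160 at 56, 0.150 at 64). The stated rule therefore does not single out 56.

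**Illustrative precision.** The exact (Clopper-Pearson) 95% limits for x passes in n tests are:
- lower = 2.5% quantile of Beta(x, n − x + 1)
- upper = 97.5% quantile of Beta(x + 1, n − x)

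When x = n the upper limit is 1.

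| Passes/tests | Observed | Exact 95% CI | Width (points, from unrounded limits) |
|---|---|---|---|
| 25/28 | 89.3% | 71.8% to 97.7% | 26.0 |
| 50/56 | 89.3% | 78.1% to 96.0% | 17.8 |
| 28/28 | 100% | 87.7% to 100% | 12.3 |
| 56/56 | 100% | 93.6% to 100% | 6.4 |

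At the same observed proportion, 26.0/17.8 = 1.46.

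The expected width at the plan's assumed proportions is the sum over x of the Binomial(n, p) probability of x times the exact width at x:

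| Assumed p | n = 28 | n = 56 | Ratio |
|---|---|---|---|
| 0.85 | 28.3 points | 19.9 points | 1.42 |
| 0.90 | 24.4 points | 17.0 points | 1.44 |
| 0.95 | 19.4 points | 13.0 points | 1.49 |

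Halving n alone would suggest a ratio near √2 = 1.41. The exact interval is a little worse than that at high proportions.

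**Independence.** Each participant has one side test, so a pooled side proportion contains no repeated results from the same person. It is a single proportion on 56 participants, as for sitting and supine.

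**The case against.** Several parts of the opposing case stand.

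- **A reader might infer that the study was sized at 56 per position and that the analysis abandons this.** Section 8.1 does not say so. It names the proportion of successful alerts, gives no width, and justifies a multiple of 8 by eight subgroups that it does not define. One test per participant per position makes the per-position reading plausible, but it remains an inference.
- **A reader might infer that the side question cannot be answered.** It can: 8.9 calls for frequencies as well as percentages, so left and right counts can be added. What is missing is a prespecified estimate. The reliability strata, however, cannot be rebuilt by adding two percentages.
- **The interval widths describe something not explicitly planned.** Section 8.9 promises 95% intervals for means, and no section sets a pass-rate criterion by position. The widening changes no planned decision.
- **Separate left and right results have a basis.** Side was randomised 28:28, and the analysis sections use four levels consistently. That supports showing both sides. It does not explain why the position named in the objective gets no result of its own.
- **A reader might infer that pooling loses nothing.** If the sides differ, the pooled figure is an average that conceals the difference. Its equal weighting also depends on 28:28 surviving replacement of withdrawals (5.3, 5.4) and listwise deletion (8.8), and the plan does not say how replacements are allocated to a side.

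**Conclusion.** The mismatch is real. Sections 1.1, 3, 4.1 and 5.4 describe three positions; 8.5.1, 8.6, 8.9 and 8.9.1 analyse four levels, and none pools left with right. The side position in the primary objective is thus reported only as two strata of 28.

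By way of illustration, an exact 95% interval for one side would be about 1.4 to 1.5 times as wide as for a position with 56 results. This assumes success proportions of 0.85 to 0.95, as in 8.1, and a completed 28:28 split.

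The point is a gap in the specification of a primary-objective result. The documents do not support the stronger claims that N=56 was set per position, that information is lost, or that pooling has no drawback. The change is worth making because it aligns the analysis with the objective, gives the side result the same denominator as the other two, and alters the position strata at almost no cost.

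**What to change.** - **8.6:** derive a three-level position (sitting, supine, side) alongside the existing four-level code.
- **8.5.1, 8.5.3, 8.9 and 8.9.1:** make the three pass proportions, each on 56 participants, the main position results, with 95% confidence intervals (exact or Wilson, named in advance). Use the three levels in the reliability strata and in the chi-square test of position.
- **Left and right:** keep both, with their difference, as a descriptive breakdown of the side result, so that pooling does not hide a side effect. Show the actual denominators in case they depart from 28.
- **8.1:** state which proportion the N=56 precision refers to, and note that left or right alone has 28. The text should not assert that 56 was chosen per position.

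The cost is one derived variable, one additional table row, the intervals, and some wording. No participants, procedures or data are added, and the left and right percentages are still shown.

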8.9.1 Analysis of Primary Endpoints

The primary goal of this research study is to assess the reliability of the FitRight® Alert Indicator for the full sample and stratified by the four rotational positions, the three different fluid amounts,

and the combination of rotational positions and fluid amounts. Cronbach's coefficient alpha estimate's reliability by determining the internal consistency of a test or the average correlation of items within a test. The pass/fail values from this set of test runs will be compared to the derived variable of whether or not the test should have triggered an alert. Since the variables of interest are dichotomous (pass/fail), the coefficient alpha is equivalent to the Kuder-Richardson 20 (KR-20) reliability measure. It produces a correlation measure between 0 where a high KR20 coefficient (e.g., >0.90) is indicative of a homogeneous test. A reliability of 0.70 or higher for an acceptable rating and 0.80 or higher for a good rating.

In addition, a chi-square analysis will be conducted to determine if any association between rotational position and test status (pass/fail) exists. This analysis will be repeated to examine any possible associations between fluid added and test status (pass/fail).

Spearman correlation analysis will be used to examine possible associations between the key variables of triggered alert value (pass/fail), rotational position (sitting, supine, left side, right side), and fluid volume of 90 mL, 150 mL, 120 mL, and 120 mL with covariates of age, sex, and brief size. Additional t-tests or non-parametric tests will be employed to further examine any significant associations found in the correlational analyses between key and covariate measures.

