4 STUDY DESIGN

4.1 Overall Design

The purpose of this study is to validate the FitRight® Sensor's ability to detect when an adult brief has absorbed enough liquid (90-360 mL normal saline via simulated urinary void) to trigger an alert to change the brief. Data will be collected from healthy, normal, adult volunteers and will be used to assess the device's absorption and ability to trigger an alert.

Each participant will be provided with the FitRight® System for the duration of the investigation. Briefs will be used to collect real-life measurement data in order to validate the FitRight® System algorithms and the FitRight® Alert Indicator.

Each participant will be measured for the appropriately sized briefs using the participant's hip dimension and will wear this size throughout the study. Three sized briefs will be worn in three different positions (sitting, laying supine, and laying on either left or right side) in order to determine the efficacy of the FitRight® Alert Indicator. Participants will apply the briefs themselves and study staff will confirm correct application. Tubing will be setup in order to apply normal saline directly to the center of the brief.

Study staff will pour 90mL normal saline (first pour) to the brief via the tubing and will start a timer for five minutes. After five minutes, study staff will record whether the FitRight® Alert Indicator triggered an alert. Note: there is no minimum volume for the alert. If the alert does trigger, participant will remove the brief and apply the next brief for the next position. If the alert did not trigger, study staff will apply 150mL normal saline (second pour) and will start a timer for five minutes. After five minutes, study staff will record whether the FitRight® Alert Indicator triggered an alert. If the alert does trigger, participant will remove the brief and apply the next brief for the next position. If the alert did not trigger, study staff will apply 120mL normal saline (third pour) and will start a timer for five minutes.

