After five minutes, study staff will record whether the FitRight® Alert Indicator triggered an alert. If the alert does trigger, participant will remove the brief and apply the next brief for the next position. If the alert did not trigger, study staff will apply 120mL normal saline (fourth pour) and will start a timer for five minutes. After five minutes, study staff will record whether the FitRight® Alert Indicator triggered an alert. Whether the FitRight® Alert Indicator triggered an alert or not, the participant will remove the brief and apply the next brief for the next position. Study staff will record whether the brief passed or failed to indicate. If the brief triggered an alert within the five minutes after the first, second, or third saline pour and prior to the fourth pour, the brief passed. If the brief did not trigger an alert by five minutes after the third pour, the brief fails. The fourth pour, if required, will help to determine if more volume was needed to trigger the alert or if the brief was defective.

The first 22 participants enrolled in the study will perform the rewet procedures. Participants will apply the sized brief and study staff will confirm correct application. Tubing will be setup in order to apply normal saline directly to the center of the brief. Study staff will pour 360 mL normal saline to the brief via the tubing and will start a timer for ten minutes. After ten minutes, participants will remove the brief and give the brief to the study staff. Study staff will weigh out at least 10.0 grams(g) filter paper (and as close to 10.0g as possible) and record the weight. Study staff will apply the filter paper centered on the wet brief and over the ADL layer, , apply a calibrated weight to the top of the filter paper, and start a timer for one minute. After one minute, the study staff will remove the calibrated weight and filter paper and weigh the wetted filter paper and record the weight. If any leakage or fluid infusion related issues occur during rewet testing this will be considered an invalid test (test failure) and this case will not be counted toward the 22 cases needed for rewet testing The data will still be recorded.

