5.4 Early Withdrawal and Replacement

Each participant will remain on the study until they have completed up to four simulated urinary void cycles in each of the 3 positions: supine, sitting, and laying on either left or right side or they are withdrawn for any reason. Participants that withdraw or are withdrawn early will be replaced. Fifty-six participants are required to successfully complete the testing. Twenty-two of the 56 participants will also perform the retest testing procedure.

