8.5 Endpoints

8.5.1. Primary Endpoint

FitRight® System alert value of pass (=1) or fail (=0), for each given value of fluid added (90, 150, 120, and 120 mL) and for each rotational position in the brief (sitting, laying supine, left side, and right side)

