8.6 Demographics, Variables and Covariates

Age will be collected as a continuous measure, with all participants being ≥ 18 years of age. Age strata will be defined as stratum 1: 18-25 years old, stratum 2: 26-41 years old, stratum 3:

42-57 years old, stratum 4: 58-67 years old, stratum 5: 68-76 years old, stratum 6: 77-94 years old, 95+ years old. Age will be considered for secondary analysis.

Sex will be collected as a categorical equal to 0=male, 1=female, 2=other, or 3=decline to answer. Sex will be considered for secondary analysis.

Brief size will be recorded as a categorical measure and will be used as a proxy for participant weight for secondary analysis.

Rotational position of the participant during the procedure will be collected as a categorical measure equal to 1=sitting, 2=supine, 3=left side or 4=right side. Rotational position will be used in the primary analysis.

Volume of simulated urine added to the brief will be collected as a categorical measure of 90 mL, 150 mL, 120 mL, and 120 mL. The volume of fluid will be used in the primary analysis.

Nominal measures of data collected will include the participant ID, date of first brief application through removal.

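### The chi-square test of position treats sitting, supine and side results from the same 56 participants as independent, and its row unit is not stated, so the direction of its error is open

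*Combined protocol and SAP*

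**What the plan says.** - **The test.** Section 8.9.1 states that "a chi-square analysis will be conducted to determine if any association between rotational position and test status (pass/fail) exists". It qualifies the chi-square no further and then repeats it for fluid added. Section 8.6 records position as a "categorical measure equal to 1=sitting, 2=supine, 3=left side or 4=right side".
- **Who supplies the data.** Section 4.1: "Three sized briefs will be worn in three different positions (sitting, laying supine, and laying on either left or right side". Section 5.4 keeps each participant in the study until "they have completed up to four simulated urinary void cycles in each of the 3 positions".
- **What is randomised.** Section 8.2 randomises "only for the side position", and "Twenty-eight patients will complete the test using their right side and 28 will complete the test using their left side". The order of sitting, then supine, then side is fixed (Sections 1.2, 6.4.1 and 6.4.2).
- **What counts as one result.** Section 4.1 scores a whole brief, with this condition for a pass: "If the brief triggered an alert within the five minutes after the first, second, or third saline pour and prior to the fourth pour". Section 8.5.1 instead defines the alert value as "pass (=1) or fail (=0), for each given value of fluid added".
- **Intervals.** Section 8.9 plans 95% intervals for means, and Section 8.1 frames N=56 around an interval for one proportion. Neither concerns a difference between positions.

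**The concern.** Pearson's chi-square assumes that every row of the table is a separate, independent observation. Here 56 people each appear under three of the four position levels. Nothing in Section 8 names McNemar, Cochran's Q, GEE, a mixed model or a clustered variance.

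Performance in three positions is part of the primary objective, and this is the only planned test that asks directly whether pass rates differ between them. A mis-specified test can err in two ways. It can miss a real difference, which might then be reported as no position effect. Or, if the rows are pours, it can declare a difference that comes only from a few non-alerting briefs being counted several times. No planned interval would show which differences remain compatible with the data.

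**Working it through.** **The plan's own figure.** The documents give no power or error figure for this test. The only design figure is N=56 for one proportion. At 85, 90 and 95% pass the full 95% Wald width at N=56 is 0.187, 0.157 and 0.114. No target width is stated, so N=56 cannot be derived, and it was not set for position differences.

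**Inputs.** From the documents: 56 participants, three briefs each (56 x 3 = 168), sides split 28/28, significance at 0.05, pass rate around 90%. Assumed, because the documents give neither: within-person correlation and the timing of alerts by pour.

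**Formulas.**
- Pearson: X² = Σ (f_j − n_j p)² / [n_j p(1 − p)], where f_j is failures in position j and p the overall failure rate.
- Cochran's Q = (k − 1)[k ΣC_j² − T²] / [kT − ΣR_i²], with k = 3, C_j failures per position, R_i failures per person and T the total.
- Bonett-Price: with p12 = (b + 1)/(n + 2), p21 = (c + 1)/(n + 2) and d = p12 − p21, the interval is d ± 1.96 √[(p12 + p21 − d²)/(n + 2)]. Here b and c are the discordant counts.

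**One row per brief.** Probit random-effect simulation, 40,000 trials per setting. Type I error is at 90% pass in every position; power is for 95% sitting v 85% supine and side. Each cell reads four-level chi-square / chi-square with sides pooled / Q.

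| Latent correlation (phi at 90% pass) | Type I error, % | Power, % |
|---|---|---|
| 0 (0) | 4.6 / 4.6 / 4.8–4.9 | 34 / 38 / 39 |
| 0.2 (0.08) | 3.8 / 3.6 / 4.8–4.9 | 33 / 37 / 42 |
| 0.3 (0.13) | 3.5 / 3.0 / 4.8–4.9 | 31 / 35 / 44 |
| 0.5 (0.25) | 2.5 / 1.9 / 4.8–4.9 | 29 / 33 / 50 |
| 0.7 (0.41) | 1.6 / 0.7 / 4.8–4.9 | 26 / 29 / 60 |

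Repeat runs agree within about half a point on type I error. For the four-level test they gave 4.4–4.8% at zero and 1.5–1.7% at 0.7; power for Q ran from 38–39% to 59–60%. The loss is best read relative to the paired test. For 95% sitting, 95% supine and 80% side, four-level chi-square power stays at 73–76% as phi goes from 0 to 0.5, while Q rises from 76% to 95%.

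**One row per pour.** Rows continue until the brief alerts, to a maximum of four, with no true position effect. A brief that alerts at once adds one pass; a brief that never alerts adds four failures in one position.

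| Assumed cumulative alerts by pour, % | False positives at correlation 0 | At latent 0.5 |
|---|---|---|
| 90, then none | 47% | 40% |
| 85, 88, 90, 92 | 39% | 28% |
| 60, 80, 90, 95 | 8.5% | 3.5% |
| 30, 70, 90, 95 | 0.5% | 0.1% |

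The highest value in a repeat run was 49%.

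**Worked example, one row per brief.** Failures 3/56 sitting, 9/56 supine, 5/28 and 4/28 on the sides; p = 21/168 = 0.125.
- Pearson: 16/6.125 + 4/6.125 + 2.25/3.0625 + 0.25/3.0625 = 4.08 on 3 df, p = 0.25.
- Q if nobody fails twice: 2[3(9 + 81 + 81) − 441]/(63 − 21) = 144/42 = 3.43, p = 0.18.
- Q with moderate overlap (one person fails all three, three fail two, twelve fail one): 144/(63 − 33) = 4.80, p = 0.09.
- Sitting-supine interval, discordant 9 v 3: d = 10/58 − 4/58 = 0.103, half-width 0.124, so −2.0 to 22.7 points. Discordant 7 v 1: half-width 0.103, so 0.0 to 20.7 points.

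All three tests are non-significant, yet a gap above 20 points is not excluded.

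**Interval width.** At 90% pass the mean Bonett-Price half-width is 11.6, 11.2, 10.9, 10.3 and 9.4 points across the five correlations; the unpaired half-width is 11.4 throughout. For left v right at 3/28 each, the Newcombe interval is ±17.9 points.

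**The case against.** The strongest reply is that little depends on this test. The main analysis in Section 8.9.1 is KR-20, no success rule uses the chi-square p-value, and the objectives ask for detection in each position rather than a comparison. Pass percentages by position are reported anyway. Against the like-for-like pooled chi-square, Q gains 1 point of power at zero correlation, 5 at latent 0.2 and 9 at 0.3. Larger gains need correlations that no section supports. The paired interval is slightly wider than the unpaired one at zero correlation (11.6 v 11.4 points). The example reaches the same verdict under every test. All of this stands, and it limits the priority of the point.

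It does not remove the point. The reply depends on one row per brief, which Section 8.9.1 does not say. Section 8.5.1 defines pass/fail by volume, and the companion test on fluid added needs rows at that level.

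A reader might infer that counting 168 results from 56 people must inflate false positives. The documents do not support that: with one row per brief and positive correlation the error goes the other way. Nor do they support the flat opposite, that the test is merely conservative, because per-pour rows can inflate error severely.

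**Conclusion.** The position test is wrong as written: it ignores the pairing of sitting, supine and side, and it does not fix its row. With one row per brief it is conservative and loses ground to a paired test, by almost nothing at zero correlation and by about 34 points of power (26% v 60%) at latent correlation 0.7 in the 95/85/85 case. With one row per pour its false-positive rate could lie anywhere from under 1% to nearly 50%. These sizes rest on assumed correlations, alert timings and pass rates.

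Left versus right is between participants, so independence is reasonable there. Even Q has modest power at N=56 for a gap of 10 points, so a non-significant result alone cannot be read as equal performance across positions. It would go too far to conclude that the study's main result or its sample size is undermined, since neither rests on this p-value.

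**What to change.** Replace the position sentence in Section 8.9.1 with:

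> One pass/fail per brief (as defined in 4.1) will be compared across sitting, supine and side (left and right combined) by Cochran's Q with participants as blocks, using participants with all three results; the number excluded will be reported. The three paired differences in pass rate will be reported with 95% confidence intervals (Bonett-Price) whatever the Q result. Pairwise mid-p McNemar tests will be run only if Q has p<0.05. Left and right (28 v 28) will be compared between participants by an uncorrected Pearson chi-square, with a 95% Newcombe interval for the difference.

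The gate on the pairwise tests matters: at 90% pass the chance that any of the three is significant is about 10% ungated at low correlation, and under 5% with the gate. For left v right a mid-p exact test would also serve, if named in advance. Fisher's test is needlessly conservative there (0.8% type I error at 90% pass, against 5.2% for uncorrected Pearson).

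State as a limitation that the fixed order confounds sitting, supine and side with sequence.

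The cost is SAP wording and slightly more analysis, with a small loss of data if some participants lack one of the three results. Data collection and N=56 are unchanged. Counterbalancing the order would be a protocol change; that and any sharing of Pods are separate matters and not part of this fix.
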